The universe of study are patients treated at the Dental Clinic of the Faculty of Dentistry of the University of Valparaíso, Chile, for rehabilitation with dental implants. Patients should be evaluated for rehabilitation by the Postgraduate Course in Oral and Maxillofacial Implantology in conjunction with surgical planning by the Postgraduate Course in Oral and Maxillofacial Surgery and Traumatology of the School of Dentistry of the University of Valparaíso. Within the inclusion criteria, participants must be between 25 and 70 years of age, requiring the installation of implants in the upper jaw and presents pneumatization of maxillary sinus of ≤ 5 mm in height (according to conebeam tomography baseline) and must sign the free and informed consent for participation in this study. Exclusion criteria are: residual edges smaller than 4 mm in height, uncontrolled systemic disease (ASA 3, 4, 5 and 6), presenting with osteoporosis or any disease of bone metabolism, having undergone radiotherapy, patients with cancer, any systemic condition that affects calcium absorption, kidney disease, having coagulation disorders, history of sinusitis, maxillary sinus pathology, heavy smoking (> 1 pack per day), drug or alcohol users, pregnancy, treatment with drugs that affect bone metabolism, treatment with immunosuppressants, allergies, uncontrolled periodontal pathology and tooth extractions in the last three months.

The sample was calculated using <https://www.sealedenvelope.com/power/continuous-superiority/>. The calculation was performed based on the results of previous studies, with a standard deviation of 5.62% for the first variable (amount of bone formed) and a difference of 6.5% between the test and control groups, obtaining an effect size of 0.98.⁶¹ Occupying this effect size with a margin of error of 0.05 and a confidence level of 90%, a sample size of 38 participants was obtained, 19 for the control group (CG) and 19 for the study group (GTP), respectively.

Projecting the withdrawal of participants add up to 2 more participants in each group, so each group will have 21 participants counting with 42 participants as a total sample.

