The implant stability coefficient (ISQ) will be evaluated by measuring the resonance frequency (Osstell ®, Göteborg, Sweden) and the insertion torque at the time of implant installation. The value of the implanted stability coefficient will be measured in two mutually perpendicular directions (distal/medial and palatine/bucal).

Statistical calculations will be performed in Prism (GraphPad Software). The parametric data obtained should be submitted to the normality test (Shapiro-Wilk test). Once the normality of the data is confirmed, the effect of the treatment will be determined by the paired t-test at 95%; Otherwise, the Mann-Whitney test should be used, considering alpha= 5%. The effect of time on the bone level in relation to baseline and the frequency of resonance will be evaluated by ANOVA or Kruskal-Walis test, depending on the normality of the data, also considering alpha= 5%. Data are expressed in terms of mean or median and 95% confidence interval.

REFERENCES

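### The sample-size figures contradict each other: 6.5/5.62 is 1.16, not 0.98, and 19 per group gives 90% power at 0.98 only with a one-sided test that the protocol does not state

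*Protocol*

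**What the plan says.** The sample-size paragraph (Protocol, Material and Methods) takes its inputs from earlier work: "a standard deviation of 5.62% for the first variable (amount of bone formed) and a difference of 6.5% between the test and control groups". It describes these as "obtaining an effect size of 0.98". It then applies that effect size "with a margin of error of 0.05 and a confidence level of 90%, a sample size of 38 participants was obtained", split 19 and 19. Two more per group are added for withdrawals, which gives 21 per group and 42 in total. The paragraph does not say whether the test is one- or two-sided.

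The statistical paragraph at the end of Material and Methods, like the abstract, sets alpha at 5% and plans a t-test, or Mann-Whitney if normality fails. On reporting it says: "Data are expressed in terms of mean or median and 95% confidence interval". Neither place mentions a one-sided test.

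**The concern.** Three things do not fit.

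1. The effect size is presented as the result of the stated SD and difference, but dividing one by the other gives a clearly larger value.
2. The number per group does not follow from either effect size under a two-sided 5% test with 90% power.
3. The labels are wrong. The 0.05 is called a margin of error and the 90% a confidence level, while the intervals to be reported are 95%. The figures make sense as a sample-size calculation only if 0.05 is alpha and 90% is power.

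This is the protocol's only justification for its size. Depending on which input is right, the trial has either more or less than its stated power, so a non-significant result could not be judged against a known target effect.

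**Working it through.** **Inputs** (sample-size paragraph): difference 6.5 percentage points; SD 5.62 percentage points (one SD only); stated effect size 0.98; alpha 0.05; power 0.90; 19 per group, raised to 21. Two-sided testing is inferred from the 5% alpha and the 95% intervals in the statistical paragraph. The calculation is for an unpaired comparison of two parallel groups.

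**Step 1: effect size.** d = difference/SD = 6.5/5.62 = 1.157. To obtain 0.98, the SD would have to be 6.5/0.98 = 6.63, or the difference 0.98 × 5.62 = 5.51. Neither figure appears in the protocol.

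**Step 2: reproducing 19 per group.** By normal approximation, n per group = 2 × [(z for alpha + z for power)/d]². The sum of z-values is 1.960 + 1.282 = 3.242 two-sided and 1.645 + 1.282 = 2.926 one-sided. The t column solves the exact noncentral-t power equation.

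| d | Test, alpha 5%, power 90% | n per group, normal | n per group, t | Total after rounding up |
|---|---|---|---|---|
| 0.98 | two-sided | 21.88 | 22.89 | 44 or 46 |
| 1.157 | two-sided | 15.71 | 16.73 | 32 or 34 |
| 0.98 | one-sided | 17.83 | 18.55 | 36 or **38** |
| 1.157 | one-sided | 12.80 | 13.54 | 26 or 28 |

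The protocol's 38 appears in one cell: d = 0.98 with a one-sided t-test. Other routes do not recover it from the stated figures:

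- Two-sided alpha of 10%, as the 90% confidence wording might suggest, leaves no stated power. With an assumed 95% power it gives 23 (normal) or 24 (t) per group at d = 0.98.
- Allowing for Mann-Whitney at d = 1.157 two-sided, with an assumed efficiency of 0.955, gives 17/0.955 = 17.8, so 18 per group and 36 in total.
- Two-sided 5% at d = 0.98 with 85% power gives 18.70 by the normal formula, which rounds to 19, but the protocol states 90%.

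**Step 3: power that the planned sample delivers** (t-test, alpha 5%).

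| d | n per group | Two-sided | One-sided |
|---|---|---|---|
| 0.98 | 19 | 83.6% | 90.6% |
| 0.98 | 21 | 87.3% | 93.0% |
| 1.157 | 19 | 93.4% | 96.8% |
| 1.157 | 21 | 95.5% | 97.9% |

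The smallest effect size detectable with 90% power, two-sided, is 1.08 at 19 per group and 1.03 at 21. Both values lie between the two candidate effect sizes.

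**The case against.** The strongest reply is that this is a reporting fault in a trial of adequate size. On the difference and SD as printed, two-sided power is 93.4% to 95.5%. Even at 0.98 with all 21 per group retained, it is 87.3%. That is correct, and it is why no larger sample is asked for. But the protocol says the calculation used 0.98, and under that value the two-sided power falls short of 90% even with no withdrawals.

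Second, a one-sided test may have been intended. The hypothesis is directional, and 38 does follow from 0.98 on that reading. This stands as the likely origin of the number. It does not settle the matter, because one-sided testing is not stated, it sits badly with 95% intervals, and it leaves the effect size at odds with its own inputs.

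Third, 0.98 could be right if 5.62 were the SD of one arm only. A pooled SD of 6.63 would then need the other arm's SD to be √(2 × 6.63² − 5.62²) ≈ 7.5. This is possible but is an assumption, since the protocol gives a single SD. It is a reason to check the source before deciding which figure to change.

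Fourth, the powers above are for an unpaired t-test, whereas the statistical paragraph names a paired t-test with a Mann-Whitney fallback. For two parallel groups the unpaired calculation is the sensible basis, but the power under Mann-Whitney would differ somewhat.

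**Conclusion.** The concern holds. The effect size does not follow from the stated difference and SD (1.157 against 0.98), whatever the sidedness or the test. The 19 per group does not follow from either effect size at two-sided 5% alpha and 90% power, which need 23 and 17 per group by t-test.

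If 0.98 is the right target, the chance of missing the effect is 16.4% with 19 per group and 12.7% with 21, against a stated 10%. If 6.5 and 5.62 are right, it is 6.6% and 4.5%. The documents do not show which input is wrong. These figures assume an unpaired two-sided t-test, equal SDs in the two groups, 0.05 as alpha and 90% as power.

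**What to change.** Rewrite the sample-size paragraph:

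- Check the SD and the difference against the cited source, and correct whichever of the three figures is wrong. If 0.98 rests on a pooled SD, state both arms' SDs and the pooled value.
- Replace the margin-of-error wording with alpha 5%, two-sided, in line with the 95% intervals, and the confidence-level wording with power. If a one-sided test was intended, say so and bring the statistical paragraph and the abstract into line.
- Keep 42 participants and state the power they give: about 93% with 19 per group (96% with 21) if the difference is 6.5 and the SD 5.62; about 84% with 19 (87% with 21) if the effect size is 0.98.

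The cost is one reworded paragraph and no additional participants. The stated power may turn out somewhat lower than 90%.

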The surgical procedures will be performed in the Surgical Center of the School of Dentistry of the University of Valparaíso by the principal investigator (maxillofacial surgeon) belonging to the Service of Oral and Maxillofacial Surgery and Traumatology of this School. All maxillary sinus augmentations should be performed by the same surgeon and assistant. Participants should be premedicated with antibiotic therapy, nasal decongestant, and anti-inflammatory drugs 24 hours prior to surgery. Fisiolimp (sodium chloride 0.9%, Pasteur Laboratory, Chile) will be indicated as a decongestant, administering a puff in each nostril every 6 hours from three days before the procedure; amoxicillin 1g (Amiotic 1 g, Laboratorio Chile, Teva) and naproxen sodium 550 mg (Laboratorio Chile, Teva), both 1 hour before surgery. For the procedure, local anesthesia will be used with Articaine 4% 1:100,000 (Septanest 4% 1:100,000, Septodont, France). A mucoperiosteal flap will be raised to access the anterior wall of

the maxillary sinus. Access to the maxillary sinus will be done through osteotomy, using a piezosurgery (VarioSurg, NSK, Nakanishi Inc, Japan) under saline irrigation. Subsequently, the Schneider membrane will be raised carefully and, according to the randomization process, the graft material (Bio-Oss® mixed with saline solution or Bio-Oss® mixed with Forteo®) will be delivered for placement on the floor of the maxillary sinus below the Schneider membrane.

Next, the access window to the maxillary sinus and the Schneider membrane will be protected with resorbable membrane of bovine collagen type I (Bio-Gide® Membrane 25x25mm, Geistlich, Dentalmax, Santiago, Chile). The mucoperiosteal flap will be repositioned and closed with Vycril 4.0 (Ethicon, J&J Surgical Technologies, USA). All patients will be indicated for postoperative Amoxicillin 1gr (Amiotic 1gr, Laboratorio Chile, Teva) 1 tablet every 12 hours for 7 days, Naproxen Sodium 550mg 1 tablet every 12 hours for 5 days (Laboratorio Chile, Teva), Paracetamol 500 mg 1 tablet every 8 hours for 3 days. All participants should be monitored 7 days after surgery for post-surgical control and radiographic control (T1).

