The installation of the implants (Mis SEVEN, Mis Implants, Mis® Implants Technologies, Israel, MBM Business Group SpA, Chile) will be planned once the images (T2) are evaluated 3 months after the graft placement. The Mis Seven implants feature a conical design, internal connection type *platform switch* and surface treated through blasting and acid attack. At this stage, the implant placement surgery should be performed by the same team of surgeons as in the first stage of the surgery. On this occasion, local anesthesia will be performed with 4% articaine 1:100,000 (Septanest 4% 1:100,000, Septodont, France). A mucoperiosteal flap will be raised in the area for implant installation and a bone core 10 mm high and 2 mm in diameter will be removed with a 2 mm trephine drill (DSP Medical, Dental Tech, Santiago, Chile). The bone biopsied through this nucleus is part of the region where the implant will be installed, and the height of the sample depends on the surgical planning previously performed (radiographic control 3 months). The sequence of drills will continue for implant placement, installation of the implant itself and finally the verification of the insertion torque and measurement of the resonance frequency with the Osstell ® (W&H; Göteborg, Sweden) in the implant already installed. The mucoperiosteal flap should be repositioned and sutured with Vycril 4.0 (Ethicon, J&J Surgical Technologies, USA). For the postoperative period naproxen sodium 550 mg 1 tablet every 12

hours for 5 days (Laboratory Chile, Teva) and Paracetamol 550 mg 1 tablet every 8 hours for 3 days. All participants should be controlled 7 days after surgery. Three months after the installation of the implants, a radiographic and clinical control (T3) will be performed to evaluate the osseointegration, graft and measurement of the resonance frequency with the Osstell®, for subsequent referral to functional and aesthetic procedures in the Post-Graduation in Oral and Maxillofacial Implantology of the School of Dentistry of the University of Valparaíso, Chile.

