For the beginning of the histological and histomorphometric analysis, the bone nuclei removed in the implant placement surgery should be fixed with 4% paraformaldehyde (PFA 4%) and stored at 4°C for 24 hours before the beginning of the laboratory procedures. These samples will be worked together with the collaborators of the Center for Biomedical Research, of the Laboratory of Morphological Analyses of the Faculty of Medicine of the University of Valparaíso.

All bone samples should be decalcified in 10% EDTA solution for 2 weeks at room temperature. Subsequently, these samples must be subjected to an ascending series of alcohol, starting 50, 70, 80, 95, 100, then Xylol. Then they should be soaked in paraffin blocks and these should be cut into serial sections 5 µm thick along the central axis of the biopsies, deparaffinized, rehydrated and stained with hematoxilin and eosin.^{23,24} Three sections of each sample should be randomly and blindly analyzed by an experienced pathologist who should perform descriptive histological analysis using a millimeter scale fitted to the 40x magnification eyepiece of a BH2 microscope (Olympus Optical Company, Ltd., Tokyo, Japan) for counting blood vessels, mesenchymal stromal cells, osteoblasts, osteoclasts, and osteocytes per mm². In addition, a histomorphometric analysis of separately quantified areas will be performed by means of a point system that should be stored in the ImageJ® SOFTWARE (NIH, USA, <http://rsb.info.nih.gov/ij>) in 10 random images captured at 10x magnification under a microscope with DP70 digital camera (Olympus) to study the following parameters: necrosis, inflammation, vascularization and angiogenesis, fibrosis, presence of medullary adipose tissue, bone neoformation and foreign body reaction. It is noteworthy that the collaborators who will work in the histological evaluation of the samples will be blind as to the attribution of the graft, because the samples donated by the participants will have a registration number that replaces the name of the participant (e.g. PARTICIPANT 1) in order to reduce the risk of bias, in addition to maintaining the anonymity

during the study. However, these antecedents are recorded in the database of the principal investigator, so it will be known to which sample each participant corresponds.

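### Random histomorphometry fields are not confined to the grafted zone, so 40–50% of a nominal 10 mm core taken from the crest would be original ridge

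*Protocol*

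**What the plan says.** All of this stands in the Protocol, Material and Methods.

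- **Ridge height.** Inclusion requires "≤ 5 mm in height (according to conebeam tomography baseline" and the exclusions begin "Exclusion criteria are: residual edges smaller than 4 mm in height". Together these leave ridges of 4 to 5 mm.
- **Graft position.** The material is delivered "for placement on the floor of the maxillary sinus below the Schneider membrane", that is, above the residual ridge.
- **Core.** At implant installation "a bone core 10 mm high and 2 mm in diameter will be removed with a 2 mm trephine drill". The core is part of the implant region, and the drill sequence for the implant continues afterwards. Its length is not strictly fixed: "the height of the sample depends on the surgical planning previously performed".
- **Sections.** They are cut 5 µm "thick along the central axis of the biopsies".
- **Reading.** Cells and vessels per mm² are counted on three sections per sample. Areas are quantified "in 10 random images captured at 10x magnification", for a list of tissue parameters that includes new bone.
- **Sizing.** The calculation uses a "standard deviation of 5.62% for the first variable (amount of bone formed") and a difference of 6.5 points between groups.

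No sentence says from which part of the core the fields or counts are taken. The Justifications section nevertheless describes the specimen as a sample of repaired bone.

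**The concern.** A section along the axis of a core taken from the crest runs through original ridge first and graft second. Fields drawn at random over that section fall in both. The drug is mixed into the graft only, so if original ridge responds less than graft (an assumption; the protocol does not say), reading it pulls the arm difference toward zero.

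The native share also differs between participants, through ridge height, core length and the chance of which fields are drawn. That adds variation unrelated to treatment. Scoring new bone as its own category does not remove the problem, because the native area still enters the area read. The cell and vessel counts per mm² have no such filter at all.

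At stake is the sensitivity of the outcome on which a trial of 38 evaluable participants was sized.

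**Working it through.** **Inputs from the protocol.** Ridge 4–5 mm; core 10 mm (nominal); 10 fields; difference 6.5 points; SD 5.62; stated effect size 0.98; 19 per group.

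**1. The plan's own sample size.** 19 per group is reproduced by a one-sided two-sample t-test with d = 0.98, alpha 0.05 and power 90%, reading the stated 90% confidence level as power. The protocol does not state the sidedness. Also, 6.5/5.62 = 1.157, not 0.98; an effect size of 0.98 implies an SD of 6.5/0.98 = 6.63. That is a separate matter, so both SDs are carried below.

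**2. Native share of the core** = ridge height / core length.
- Nominal core: 4/10 = 40% to 5/10 = 50%.
- If core length ran from 8 to 12 mm (assumed range): 4/12 = 33% to 5/8 = 63%.

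**3. Native fields among 10.** The expected number is 10 × 0.4 = 4 to 10 × 0.5 = 5. If fields fall independently (assumption), the count is binomial:
- SD = √(10 × 0.4 × 0.6) = 1.55 to √(10 × 0.5 × 0.5) = 1.58 fields.
- 5th–95th percentile: 2–7 at 40%, 2–8 at 50%.

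**4. Illustration of the power loss.** Assume that 6.5 points refers to grafted tissue, native bone does not respond and the SD is unchanged. Expected difference = 6.5 × (1 − native share). Power is for a two-sided t-test, alpha 0.05, 19 per group.

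| Native share | Difference | Power, SD 5.62 | Power, SD 6.63 |
|---|---|---|---|
| 0 | 6.5 | 93.4% | 83.6% |
| 40% | 3.9 | 54.8% | 42.2% |
| 50% | 3.25 | 41.1% | 31.2% |

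**5. The same, letting the SD shrink.** Suppose native fields score zero new bone. With native share S (mean f) and graft value G, the reading is (1 − S)G, with variance [(1 − f)² + Var(S)] × 5.62² + Var(S) × mean(G)². Take control means of 10% to 25% (assumed), the test mean 6.5 points higher, and the average of the two arm variances.
- Independent fields, Var(S) = f(1 − f)/10: power 55–82% at f = 40%, 44–76% at f = 50%.
- Fields spread evenly, SD of S taken as 0.05 (assumed): power 87–92% over both shares.
- S constant: difference and SD shrink by the same factor and power stays at 93.4%.

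**6. After the fix.** The grafted zone of a 10 mm core is 10 − 5 = 5 to 10 − 4 = 6 mm. If the border is set too crestal by an assumed 0.5 mm, the native share of what is read is 0.5/6.5 to 0.5/5.5 = 8–9%. At 1 mm it is 1/7 to 1/6 = 14–17%.

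**The case against.** The strongest reply is that the protocol is silent here, not wrong. Random images are specified without saying over what area. The stated targets (newly formed bone, repaired bone, repair of the sinus floor augmentation) would let a reader stay within the graft and still comply. The histology text also cites two published comparisons after sinus augmentation, which may define a zone. **In part this stands:** the protocol does not instruct anyone to read native ridge. But the citation sits on the sectioning and staining sentence, not on field selection. And core orientation has to be kept at removal; no later analysis plan can restore it.

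Second, the size of the loss is unknown. The 6.5 points and their SD come from a cited study that is not at hand, and they may already describe whole cores. Holding the SD at 5.62 is a pessimistic corner, as step 5 shows. **This stands**, and is why the 41–55% is only an illustration.

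Third, the range of 2 to 8 native fields needs fully independent placement; non-overlapping fields along one core would vary less. **This stands too**, but the expected share of 40–50% does not depend on it.

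Fourth, a border taken from T0 imaging assumes that the trephine follows the axis of the T0 measurement, that the crest is stable over three months, and that the core is intact after decalcification. **This is a real limit of the remedy.** An error in the apical direction would discard some graft.

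**Conclusion.** The concern holds. Under the protocol's own dimensions, and given entry from the crest, 40–50% of the nominal core is ungrafted ridge, and the sampling rule as written does not exclude it. Crestal entry is inferred from the implant-bed location and the continuing drill sequence; it is not stated.

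The consequence for power cannot be fixed from the protocol. It runs from none (if the planning difference came from whole cores, or the SD shrinks in proportion) to substantial. There is no bias between arms and no added risk of a false positive. This should be corrected; confidence is medium, because the effect depends on how native bone responds and is scored.

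**What to change.** In Material and Methods, add to the biopsy and histology text:

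1. Mark the crestal end of each core at removal.
2. Define the region of interest as the part of the core beyond the site's T0 residual height, measured from the marked end. The imaging text already measures that height at the graft and implant site. Because T0 precedes treatment, the border cannot depend on arm. Apply it identically in all cores, blind to allocation.
3. Draw the 10 random fields and make the cell and vessel counts only within that region. Report the native part separately.
4. Do not set the border by where graft particles appear. The Justifications section expects teriparatide to reduce them, so such a border would depend on treatment.
5. Optionally, skip one fixed margin (for example 1 mm) beyond the border in every core.

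**Cost.** An orientation mark and a few sentences; the cores, sections, scans and blinded reader stay the same. The area to sample shrinks to 5–6 mm of a 10 mm core, or 4–5 mm with a 1 mm margin. Shrinkage, fragmentation or mismatch between scan and section will cause some border error. At an assumed 0.5–1 mm too crestal, 8–17% of what is read would still be native, against 40–50% now.

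### A normality pre-test on the trial's own data decides whether the mean difference in bone formation, on which the trial is sized, is the quantity tested

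*Protocol*

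**What the plan says.** The last paragraph of MATERIAL AND METHODS in the Protocol sets a two-step rule, and the abstract carries the same rule.

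- Step 1: "The parametric data obtained should be submitted to the normality test (Shapiro-Wilk test").
- Step 2, if the data pass: "Once the normality of the data is confirmed, the effect of the treatment will be determined by the paired t-test at 95"%.
- Step 2, if they do not: "Otherwise, the Mann-Whitney test should be used, considering alpha= 5"%.
- Reporting: "Data are expressed in terms of mean or median and 95% confidence interval".

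The time effect on bone level and resonance frequency is gated in the same way: it "will be evaluated by ANOVA or Kruskal-Walis test, depending on the normality of the data".

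The sample-size paragraph of the same section works with means. It takes a "standard deviation of 5.62% for the first variable (amount of bone formed") and "a difference of 6.5% between the test and control groups", and arrives at 19 participants per group, raised to 21 for withdrawals.

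No sentence exempts bone formation from the pre-test. The significance level of the Shapiro-Wilk test is not given, nor is it said whether each arm, the pooled data or the residuals are tested.

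**The concern.** The same small sample first chooses the test and is then tested. At this size a non-significant Shapiro-Wilk result does not confirm normality, and a significant one arises by chance in data that are normal.

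The switch also changes the question. The t-test branch compares means. The Mann-Whitney branch compares rank order, and a median may then be the summary. The trial was sized to detect a difference in means, yet the protocol leaves it to the data whether that difference is what the treatment test addresses. Two trials run identically could report bone formation on different effect measures, and neither measure could be named beforehand.

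This is a rule that the protocol states, not a detail left open for a statistical analysis plan. A plan that followed the protocol would inherit it.

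**Working it through.** **1. The sizing is a comparison of means.** Inputs from the sample-size paragraph: stated effect size 0.98, error 0.05, 90% (read as power), two equal groups. A two-sample t-test calculation, one-sided at 0.05, needs 18.55 per group, which rounds up to 19 and gives 2 × 19 = 38, the protocol's figure. The two-sided version needs 22.89, so 23 per group. The stated difference and SD give 6.5 / 5.62 = 1.157, not 0.98. That mismatch is a separate matter. On either effect size the quantity is a difference in means.

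**2. Chance of a switch when the data are normal.** Assume Shapiro-Wilk at 5% in each arm, with one significant result enough to switch:

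1 − 0.95² = 0.0975, about 10%.

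Simulation (5,000 trials) gives 10.1% at 19 per arm and 9.8% at 21. If one test is run on pooled residuals instead, the rate is about its own level, 5%.

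**3. Chance of a switch under assumed shapes.** The documents give neither a distribution nor a mean for bone formation, so every shape below is an assumption. The pre-test is again at 5% in each arm.

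| Assumed shape in both arms | 19 per arm | 21 per arm |
|---|---|---|
| Normal | 10.1% | 9.8% |
| Gamma, mean 15, SD 5.62 | about 32% | not run |
| t with 5 df | 33% | 36% |
| Lognormal, sigma 0.3 | 41% | 45% |
| Gamma, shape 4 | 47% to 49% | 52% |
| Lognormal, sigma 0.5 | 74% | 80% |

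The first gamma has shape (15 / 5.62)² = 7.12 and skewness 2/√7.12 = 0.75. Gamma shape 4 has skewness 2/√4 = 1. Mild to moderate skew therefore switches roughly 30% to 50% of trials. The last row is a stronger skew.

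**4. Effect on alpha.** With identical distributions in both arms, and an unpaired t-test in the first branch, the two-step rule rejects in 4.8% to 5.8% of simulated trials across scenarios. The Monte Carlo standard error is √(0.05 × 0.95 / 5,000) = 0.3 points.

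**5. Effect on power at the design effect.** 19 per arm, unpaired, simulated:

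| Scenario | Welch | Two-step rule |
|---|---|---|
| Normal, 6.5 / 5.62 | 93.8% | 93.7% |
| Gamma (mean 15, SD 5.62), difference 6.5 | 93.8% | 94.8% |
| Normal, d = 0.98 | 82.9% | 82.6% |
| Gamma, d = 0.98 | 83.0% | 84.4% |

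The differences run from −0.3 to +1.4 points, so the rule costs no material power.

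**The case against.** The best defence is that the rule is written down in advance, is common practice, and does no measurable harm to the inference. On alpha and power that defence stands, as the figures above show. What it does not answer is that the two branches test different things, and only one of them matches the sizing.

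Four stronger readings are tempting, and the documents do not support them.

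- **Visits of one outcome end up on different tests.** With p = 0.0975 per visit and three independent visits, 1 − p³ − (1 − p)³ = 26%. That needs a separate treatment test at each visit and a separate pre-test in each arm. The protocol prescribes neither, and for the time effect it names one analysis per outcome. With pooled residuals the figure would be 14%.
- **The mean difference is never produced in the rank branch.** The reporting sentence does not tie the median to Mann-Whitney, does not say that the intervals are per arm, and does not exclude an interval for the difference. A statistical analysis plan that is not shown could supply one.
- **The choice is a coin-flip.** It nears 50% only under assumed shapes. Under normality it is 5% to 10%.
- **The gate inflates false positives.** With equal means but gamma shapes 8 and 2, the two-step rule rejects in 10.6% of trials. Plain Mann-Whitney does so in 10.8%, so the excess comes from the rank test under unequal spread. At mean 15 the SDs would be 15/√8 = 5.3 and 15/√2 = 10.6, whereas the protocol plans with a single SD.

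**Conclusion.** The point holds as a modest one that is cheap to correct. The protocol fixes a data-driven rule under which the mean difference in bone formation may or may not be the quantity tested.

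The size of the problem is the switch rate: about 10% with normal data if each arm is tested at 5%, about 5% if pooled residuals are tested, and about 30% to 50% under assumed mild to moderate skew. These rates rest on an assumed pre-test level and unit and, beyond the normal case, on assumed distributions. Alpha with identical distributions and power at the design effect are essentially unchanged. The damage is confined to the consistency of the effect measure between the sizing, the test and the report.

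**What to change.** In the abstract and in the statistical paragraph of MATERIAL AND METHODS, delete the normality gate for the treatment comparison and name one primary between-arm analysis in advance: the difference in means from an unpaired unequal-variance (Welch) comparison or a linear model, with its 95% CI. It must be unpaired because the two randomised groups are independent. Calling the t-test paired is a separate error in the same sentence.

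Keep Mann-Whitney as a sensitivity analysis, reported with the Hodges-Lehmann shift and its 95% CI.

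If any of the histological cell counts are to be analysed on another scale, list those variables and the scale by name beforehand. A clause triggered by observed skew would bring the same data-dependent choice back.

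The cost is wording only. The change itself leaves 19 per group (21 with the allowance) as it is, since the sizing is already in means. The downside is slightly lower efficiency for heavily skewed counts, which the sensitivity analysis partly covers.
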